1 PROTOCOL SUMMARY

1.1 SYNOPSIS

Protocol title:

A Phase 3, randomized, double-blind, placebo-controlled, parallel-group study to evaluate the efficacy and safety of tolebrutinib (SAR442168) in adults with generalized myasthenia gravis

Brief title:

Efficacy and safety of tolebrutinib (SAR442168) tablets in adult participants with generalized myasthenia gravis

Rationale:

There is an unmet need for people with generalized myasthenia gravis (gMG) for effective treatments with better long-term safety profiles and with more feasible modes of administration. Tolebrutinib (SAR442168), a covalent, irreversible inhibitor of Bruton's tyrosine kinase (BTK), is an immunomodulatory agent relevant to the pathophysiology of gMG that has the advantage of oral administration.

See Study Rationale, [Section 2.1](#).

Objectives and endpoints

	Objectives	Endpoints
Primary		
DB period	To evaluate the efficacy of tolebrutinib 60 mg daily compared to placebo as measured by MG-ADL score in participants with gMG who are receiving SoC	Change from baseline in MG-ADL total score at Week 26
OLE	To evaluate the long-term safety and tolerability of tolebrutinib 60 mg daily in participants with gMG who are receiving SoC	AEs, serious AEs, AEs leading to permanent study intervention discontinuation, AESIs, potentially clinically significant abnormalities in laboratory tests, ECG, and vital signs during the treatment period
Secondary		
DB period	To evaluate the efficacy of tolebrutinib 60 mg daily compared to placebo on additional efficacy measurements: QMG, MGII, MG-QoL15, MG-ADL in participants with gMG who are receiving SoC	Change from baseline in QMG total score at Week 26 Change from baseline in MG-ADL total score at Week 12 [REDACTED] Change from baseline in MGII total score at Week 26 Change from baseline in MG-QoL15 total score at Week 26 Proportion of participants with \geq 2-point improvement (reduction) in MG-ADL total score at Week 26 Proportion of participants with \geq 3-point improvement (reduction) in QMG total score at Week 26

Objectives	Endpoints
To evaluate the safety and tolerability of tolebrutinib 60 mg daily compared to placebo in participants with gMG who are receiving SoC	AEs, serious AEs, AEs leading to permanent study intervention discontinuation, AESIs, potentially clinically significant abnormalities in laboratory tests, ECG, and vital signs during the treatment period
OLE	
To evaluate the long-term efficacy of tolebrutinib 60 mg daily in participants with gMG who are receiving SoC	Change from baseline in MG-ADL total score over time Change from baseline in QMG total score over time Change from baseline in MGII total score over time Change from baseline in MG-QoL15 total score over time Proportion of participants with ≥ 2 -point improvement (reduction) in MG-ADL total score at EOT (timeframe: baseline, up to Week 130) Proportion of participants with ≥ 3 -point clinical improvement (reduction) in QMG total score at EOT (timeframe: baseline, up to Week 130) Proportion of participants achieving any reduction from baseline of daily dose of OCS over time

[REDACTED]; AE: adverse event; AESI: adverse event of special interest; DB: double-blind; ECG: electrocardiogram; EOS: end of study; EOT: end of treatment; gMG: generalized myasthenia gravis; [REDACTED]
[REDACTED]; MG-ADL: Myasthenia Gravis Activities of Daily Living; [REDACTED]
[REDACTED] MG-QoL15: Myasthenia Gravis Quality of Life 15-item scale; MGII: Myasthenia Gravis Impairment Index;
MuSK: muscle-specific kinase; OCS: oral corticosteroid; OLE: open-label extension; PD: pharmacodynamic; PK: pharmacokinetic; QMG: Quantitative Myasthenia Gravis; QoL: quality of life; SoC: standard of care.

For China, please see [Section 10.8](#) for details.

Overall design:

EFC17262 is a multicenter, randomized, double-blind (DB), placebo-controlled, Phase 3 study to evaluate the efficacy and safety of tolebrutinib 60 mg daily compared with placebo in participants aged 18 to 85 years with moderate-to-severe gMG who are receiving the standard of care (SoC). The DB period will be followed by an open-label extension (OLE) period to evaluate the safety and efficacy of tolebrutinib.

[figure not shown]
The DB period will include a screening period (up to 28 days) and a treatment period of 26 weeks. After screening, eligible participants will be randomly assigned (1:1 ratio) to receive 60 mg of a tolebrutinib oral, daily dose or matching placebo. Randomization will be stratified by the Myasthenia Gravis Foundation of America (MGFA) class (II, IIIa/ IVa, or IIIb/IVb) and region (United States [US], non-US). The primary endpoint will be change from baseline in the Myasthenia Gravis-Activities of Daily Living (MG-ADL) score at Week 26.

Participants will receive the investigational medicinal product (IMP) as an add-on therapy to their SoC, ie, their gMG treatment(s) prior to screening maintained at stable doses throughout the 26-week duration of the DB period. These treatments are required to be at a stable dose for a predefined duration prior to the entry in the study; see details in the inclusion criteria ([Section 5.1](#)). The SoC may consist of an acetylcholinesterase inhibitor (AChEI) (eg, pyridostigmine), oral corticosteroids (OCS) up to the maximal dose of 20 mg daily, and/or

a single immunosuppressive treatment (IST), such as azathioprine, mycophenolate mofetil, tacrolimus, or methotrexate.

However, the use of rescue therapy for gMG worsening will be allowed at the discretion of the Investigator if there is at least a 2-point increase of individual non-ocular MG-ADL items compared to the Day 1 MG-ADL score, or new or worsening of respiratory/ bulbar symptoms. Rescue therapy can include intravenous immunoglobulin (IVIg), plasma exchange, change in the SoC, OCS dose, or any use of new corticosteroids (CS). If rescue therapy is needed, the Sponsor should be informed, preferably prior to the administration of treatment, where possible, without compromising the participant's safety (see [Section 6.8.3](#)). In case of use of rescue therapy during the DB period, the study intervention will be permanently discontinued.

If a participant prematurely and permanently discontinues treatment with the IMP during the DB period, the participant will be asked to perform a premature end-of-treatment (pEOT) visit and to continue to perform DB period visits without IMP. If the participant is not willing to continue with DB study visits without IMP, there will be a safety follow-up (FU) period (4 to 8 weeks) after the pEOT visit.

All participants who complete the DB period on treatment will enter the OLE. During this study period, all participants will receive open-label tolebrutinib 60 mg daily while continuing to receive the same SoC treatment. However, during the OLE, SoC treatments may be adjusted (ie, dose change, discontinuation, or addition of other allowed SoC treatments) at the discretion of the Investigator based on the clinical presentation. Rescue therapy medications will also be allowed during the OLE, as described in [Section 6.8.3](#), and participants using rescue therapy during the OLE will not be required to discontinue study intervention. Please refer to [Section 6.8](#) for drugs that will continue to be prohibited during the OLE. The OLE will include a safety FU period (4 to 8 weeks) upon discontinuation of open-label IMP, prematurely or at the premature end of study (EOS).

An IDMC will review the safety data of participants in the study and advise the Sponsor on the conduct of the clinical study.

Brief summary:

This is a multicenter, randomized, DB, placebo-controlled, Phase 3 study to evaluate the efficacy and safety of tolebrutinib 60 mg daily compared with placebo in adult participants aged 18 to 85 years with moderate-to-severe gMG who are receiving the SoC. The DB treatment period of 26 weeks will comprise 7 site visits followed by a 2-year OLE period with quarterly visits. The efficacy of tolebrutinib versus placebo during the DB period will be assessed by clinical evaluations, which include scales based on the physician's examination or direct participant feedback, ie, clinical outcome assessments. These evaluations will continue during the OLE in order to measure long-term efficacy and safety.

Number of participants:

Approximately █ people will be screened to achieve █ participants randomized to the study intervention at a randomization ratio of 1:1 (assuming a screen failure rate of 20%).

Intervention groups and duration:

The DB period will include a screening period (up to 28 days), after which eligible participants will be randomized to a treatment group, 60 mg oral, daily tolebrutinib or matching placebo. The duration of the treatment period will be 26 weeks.

The OLE will include all eligible participants who have completed the DB period on treatment. Participants will receive 60 mg of oral, daily tolebrutinib for a duration of up to 2 years.

Post-trial access may be considered, if required, and approved by local regulations.

Study intervention(s)

Investigational medicinal product

- Formulation: tolebrutinib film-coated tablet
- Route of administration: oral
- Dose regimen: 60 mg once daily taken with a meal

Investigational medicinal product

- Formulation: placebo to match tolebrutinib film-coated tablet
- Route of administration: oral
- Dose regimen: once daily taken with a meal

Noninvestigational medicinal products(s)

- Not applicable.

Devices

Not applicable.

Post-trial access to study medication

Post-trial access may be considered, if required, and approved by local regulations.

Statistical considerations:

The modified intention-to-treat (mITT) population will include all randomized and treated participants with a baseline value and at least 1 post-baseline value for any efficacy assessment. Participants will be analyzed as randomized. This will be the primary efficacy population.

- **Primary endpoint (DB period):**

A combination of treatment policy strategy and composite variable strategy will be used to handle intercurrent events (ICEs) for the analysis of the primary endpoint of change from baseline in MG-ADL total score at Week 26 in the mITT population (see [Table 5](#)).

Population level summary: Difference in mean change from baseline MG-ADL total score between tolebrutinib and placebo will be analyzed using an analysis of covariance (ANCOVA) with change from baseline MG-ADL total score at Week 26 as the response variable, accounting for ICEs as detailed in [Table 5](#); and treatment, baseline MG-ADL total score, and all randomization stratification factors as covariates. For participants who prematurely discontinue study intervention due to a reason other than rescue therapy or lack of efficacy and then further withdraw from the study before Week 26, their MG-ADL total score will be missing at Week 26 and therefore will not be included in the ANCOVA model. Difference in least squares means, the corresponding 95% confidence intervals (CIs) and p-value will be provided for the comparison of tolebrutinib versus placebo.

- **Main secondary endpoints (DB period):**

The primary analysis of the main secondary efficacy endpoints, change from baseline in QMG total score at Week 26, and change from baseline in Myasthenia Gravis Impairment Index (MGII) total score at Week 26, will be based on a combination of treatment policy strategy and composite variable strategy in the mITT population.

These secondary endpoints will be analyzed in the same way as the primary endpoint, except that the respective baseline value corresponding to the endpoint will be included as the covariate in the ANCOVA model and the worst change from baseline value as stated in [Section 9.3.2](#) for participants who permanently discontinue study intervention due to rescue therapy and/or lack of efficacy will be based on the corresponding assessment.

[figure not shown]
Data Monitoring Committee: Yes

Scientific Advisory Committee: Yes

Independent Hepatology Assessment Committee: Yes

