3 OBJECTIVES AND ENDPOINTS

Table 1 - Objectives and endpoints

Objectives	Endpoints
Primary	
DB period	
To evaluate the efficacy of tolebrutinib 60 mg daily compared to placebo as measured by MG-ADL score in participants with gMG who are receiving SoC	Change from baseline in MG-ADL total score at Week 26
OLE	
To evaluate the long-term safety and tolerability of tolebrutinib 60 mg daily in participants with gMG who are receiving SoC	AEs, serious AEs, AEs leading to permanent study intervention discontinuation, AESIs, potentially clinically significant abnormalities in laboratory tests, ECG, and vital signs during the treatment period
Secondary	
DB period	
To evaluate the efficacy of tolebrutinib 60 mg daily compared to placebo on additional efficacy measurements: QMG, MGII, MG-QoL15, MG-ADL in participants with gMG who are receiving SoC	Change from baseline in QMG total score at Week 26 Change from baseline in QMG total score at Week 12 (for the interim analysis only) Change from baseline in MGII total score at Week 26 Change from baseline in MG-QoL15 total score at Week 26 Proportion of participants with ≥ 2 -point improvement (reduction) in MG-ADL total score at Week 26 Proportion of participants with ≥ 3 -point improvement (reduction) in QMG total score at Week 26 AEs, serious AEs, AEs leading to permanent study intervention discontinuation, AESIs, potentially clinically significant abnormalities in laboratory tests, ECG, and vital signs during the treatment period
OLE	
To evaluate the safety and tolerability of tolebrutinib 60 mg daily compared to placebo in participants with gMG who are receiving SoC	Change from baseline in MG-ADL total score over time Change from baseline in QMG total score over time Change from baseline in MGII total score over time Change from baseline in MG-QoL15 total score over time Proportion of participants with ≥ 2 -point improvement (reduction) in MG-ADL total score at EOT (timeframe: baseline, up to Week 130) Proportion of participants with ≥ 3 -point clinical improvement (reduction) in QMG total score at EOT (timeframe: baseline, up to Week 130) Proportion of participants achieving any reduction from baseline of daily dose of OCS over time

Objectives	Endpoints

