8.1.1.2 Quantitative Myasthenia Gravis (QMG) Test

The Quantitative Myasthenia Gravis test is clinician-reported outcome/assessment to assess muscle weakness in people with MG. The QMG test consists of 13 items ranging from 0 to 3 with 3 being the most severe. A total QMG score ranges from 0 to 39, where higher scores indicate greater disease severity. The QMG score is composed of the following items: ocular (2 items), facial (1 item), bulbar (2 items), gross motor (6 items), axial (1 item), and respiratory (1 item). Clinically significant changes have been reported as follows: in mild (QMG score 0 to 9) to moderate (QMG score 10 to 16) MG, a 2-point change has been reported as clinically significant. For more severe (QMG score >16) MG, a 3-point change has been reported as clinically significant ([42](#)). Change from baseline in QMG score at Week 12 will be used for the IA based on its correlation to MG-ADL. Acetylcholinesterase inhibitors will be held at least 12 hours prior to QMG test administration at each study visit. The QMG test shall be administered at approximately the same time of day throughout the study at the protocol specified timepoints. See Appendix 11 ([Section 10.11.2](#)).

[figure not shown]

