9 STATISTICAL CONSIDERATIONS

The data from the placebo-controlled and the OLE treatment phases will be the focus of the clinical study report of the respective phase. The following statistical methods/considerations relate to the analysis of the data from the placebo-controlled period. The data from the open-label portion are non-controlled and supportive in nature; summary statistics will be provided for each of the efficacy variables and for safety data.

The null hypothesis for the primary efficacy endpoint of the change from baseline in MG-ADL score at Week 26 is that there is no treatment difference between tolebrutinib and placebo, and the alternative is that there is a between-treatment difference. To strongly control the type I error rate for the study, a procedure will be applied at a 2-sided 5% significance level. If tolebrutinib is significant for the primary endpoint, a selective set of secondary endpoints will be tested following a pre-specified procedure. The complete list of the secondary endpoints that will be adjusted for multiplicity will be detailed in the statistical analysis plan (SAP) prior to the interim database lock. The study will be declared positive at the final analysis if the null hypothesis for the change from baseline in MG-ADL score at Week 26 for tolebrutinib versus placebo is rejected.

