9.3 STATISTICAL ANALYSES

The SAP will be finalized prior to the database lock for the IA and will include more technical and detailed descriptions of the statistical analyses, including methods to assess the impact of missing data, subgroup analyses, etc. This section is a summary of the planned statistical analyses of the most important endpoints including primary and secondary endpoints.

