9.3.3 Secondary endpoints

The secondary efficacy endpoints are listed in the objectives and endpoints table (see [Table 1](#)). Primary analyses of secondary endpoints will be based on a combination of treatment policy strategy and composite variable strategy in the mITT population.

Secondary efficacy endpoints, defined as change from baseline score at Week 26, will be analyzed in the same way as the primary endpoint, except that the respective baseline value corresponding to the endpoint will be included as the covariate in the ANCOVA model and the worst change from baseline value as stated in [Section 9.3.2](#) for participants who permanently discontinue study intervention due to rescue therapy and/or lack of efficacy will be based on the corresponding assessment.

The proportion of responders, defined as a ≥ 2 -point reduction in MG-ADL score at Week 26, will be analyzed using a Cochran-Mantel-Haenszel test, stratified by at least the randomization stratification factors, in the mITT population. Participants not reaching at least a 2-point reduction at Week 26 or permanently discontinuing study intervention due to rescue therapy and/or lack of efficacy will be considered non-responders. The relative risk comparing tolebrutinib versus placebo will be provided along with the corresponding 95% CI. The same analysis approach will be used for the proportion of responders based on QMG score; a ≥ 3 -point reduction in QMG score at Week 26.

Data collected after the premature discontinuation of study intervention will be included for supplementary analyses for the main secondary endpoints to assess the efficacy of tolebrutinib compared to placebo in an ITT setting, ie, the assessment of the treatment policy or strategy, using the same MMRM as stated for supplementary analysis of the primary endpoint in [Section 9.3.2](#), except that the respective baseline value corresponding to the endpoint will be included as the covariate. Details, including any subgroup analyses, will be included in the SAP.

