10.1.5 Committee structures

10.1.5.1 *Independent Data Monitoring Committee*

An IDMC, operating independently of the Sponsor and clinical Investigators, will be responsible for overseeing the safety of participants throughout the study. This committee is composed of externally based individuals with expertise in the disease under study, biostatistics, or clinical research. The primary responsibilities of the IDMC are to review and evaluate the safety data and to make appropriate recommendations to the Sponsor regarding the conduct of the clinical study.

[figure not shown]
Details describing the IDMC processes and procedures are outlined in the IDMC charter. To maintain continuous blinding and study integrity, the analysis, including the IA developed in [Section 9.4](#), will be conducted by an independent statistical group who will directly transfer data to IDMC members, and measures will be taken to ensure the validity of the data.

The IDMC will review the unblinded results of the IA, provided by the independent statistical group, and recommend the Sponsor (therapeutic area head or development head only) of the next steps based on the pre-specified criteria.

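### Does the synopsis row for MG-ADL at Week 12, where Table 1 has QMG at Week 12, leave a secondary endpoint without an analysis?

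*Combined protocol and SAP*

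**What the plan says.** The synopsis (section 1.1), under the secondary objectives of the double-blind period, has as its second efficacy entry "Change from baseline in MG-ADL total score at Week 12". A blacked-out span follows it.

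Table 1 (section 3) has in the same position "Change from baseline in QMG total score at Week 12 (for the interim analysis only".

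Section 8.1.1.2, in running text, agrees with Table 1: "Change from baseline in QMG score at Week 12 will be used for the IA based on its correlation to MG-ADL".

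Section 9.3.3 says where its endpoints come from: "The secondary efficacy endpoints are listed in the objectives and endpoints table", with a cross-reference to Table 1. It then defines the change-score analysis: "Secondary efficacy endpoints, defined as change from baseline score at Week 26, will be analyzed in the same way as the primary endpoint". The two responder endpoints, also at Week 26, get a Cochran-Mantel-Haenszel test.

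The multiplicity list is left to a later document: "The complete list of the secondary endpoints that will be adjusted for multiplicity will be detailed in the statistical analysis plan (SAP". Its timing is given in section 9.3: "The SAP will be finalized prior to the database lock for the IA". Section 10.1.5.1 refers the interim analysis to section 9.4, which is not in the public text.

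**The concern.** The two endpoint lists serve the same objective and should be identical. They name different instruments at Week 12. MG-ADL is an interviewer-administered scale of daily function scored 0 to 24 (section 8.1.1.1). QMG is a clinician-assessed test of muscle weakness scored 0 to 39 (section 8.1.1.2).

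Taken literally, the synopsis creates a secondary endpoint with no row in Table 1 and no method in section 9.3.3, and its visible list omits the variable meant for the interim analysis. If a reader could not tell which list governs, MG-ADL at Week 12 might be added to or dropped from the reported secondary endpoints after data had been seen. Doubt about the interim variable would be more serious, because the IDMC is to act on pre-specified criteria.

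**Working it through.** No arithmetic beyond counting applies, so the check sets the passages side by side.

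**Step 1. Compare the visible efficacy lists for the double-blind period.**

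| Entry | Synopsis | Table 1 | Analysis in 9.3.3 |
|---|---|---|---|
| 1 | QMG change, Week 26 | same | ANCOVA |
| 2 | MG-ADL change, Week 12 (blacked-out text follows) | QMG change, Week 12, interim only | none for either |
| 3 | MGII change, Week 26 | same | ANCOVA |
| 4 | MG-QoL15 change, Week 26 | same | ANCOVA |
| 5 | MG-ADL responders, Week 26 | same | Cochran-Mantel-Haenszel |
| 6 | QMG responders, Week 26 | same | Cochran-Mantel-Haenszel |

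Matching entries: 5 of 6. Differing entries: 1 of 6.

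**Step 2. Count the entries with an analysis in section 9.3.3.** Synopsis: 3 (ANCOVA) + 2 (Cochran-Mantel-Haenszel) = 5 of 6. Table 1: 3 + 2 = 5 of 6. The count is the same for both lists. The missing Week 12 analysis therefore does not separate the disputed entry from the accepted one. An interim-only variable would naturally be handled in section 9.4 or the SAP.

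**Step 3. Ask which list governs.** Section 9.3.3 points to Table 1. Section 8.1.1.2 independently names QMG at Week 12 and justifies it by its correlation with MG-ADL, which makes sense only if the interim variable is not MG-ADL itself. The statistical text of the synopsis mentions MG-ADL, QMG and MGII at Week 26 only. The synopsis row is the outlier.

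**Step 4. Allow for the blacked-out span.**
- If it hides an interim-only qualifier, the synopsis names the wrong instrument for a variable that Table 1 and section 8.1.1.2 both identify as QMG.
- If it hides a further row, such as QMG at Week 12, then MG-ADL at Week 12 is an extra synopsis line with no match in the visible Table 1.

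In both cases section 9.3.3 still sends the analyst to Table 1.

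**Step 5. Trace the consequences.** The primary endpoint and the sample-size assumptions (difference of -2, SD of 4) concern MG-ADL at Week 26. The visible text sets no testing order for secondary endpoints; that is left to the SAP. Both scales appear to be scheduled at Week 12 in the schedule of activities, although its columns are partly broken in the extracted text. The supplementary MMRM in section 9.3.2 already uses MG-ADL at scheduled visits with a treatment-by-visit term, though its stated inference is at Week 26. No visible analysis depends on the synopsis row.

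**The case for a change.** The strongest case for acting is that the protocol contradicts itself in current text, and neither the redaction nor broken table extraction can turn QMG into MG-ADL. One SAP cannot agree with both lists. The amendment history shows the synopsis and section 3 being edited together, so the sponsor means them to agree. The correction would take one line, and the natural deadline is the interim database lock.

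Most of that stands as description: the inconsistency exists and the synopsis is the likely source. What does not stand is the claimed harm. A reader can tell which list governs, because section 9.3.3 says so. Nothing in the protocol gives the synopsis table precedence over the sections it summarises. The argument from the absent analysis applies equally to QMG at Week 12, so it proves too much. It is also too strong to say that the synopsis defines a full secondary endpoint, since the hidden text may restrict it. The visible Table 1 is itself disordered in extraction, so a statement about what it omits can cover only the text that can be read.

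**Conclusion.** The mismatch is a clerical slip in a summary table and calls for no change to the plan. Its size is 1 of 6 visible secondary efficacy entries. It has no shown effect on the primary analysis, the Week 26 secondary analyses, type I error, power, the interim rule or data collection. An analyst who follows the body text reaches one answer: QMG at Week 12, for the interim analysis. Aligning the synopsis row when the protocol is next amended would be tidy, but it would alter no result or conclusion.

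This rests on two assumptions that the public text cannot confirm: that section 9.4 and the SAP use QMG at Week 12 for the interim analysis, as Table 1 and section 8.1.1.2 do, and that MG-ADL at Week 12 is not in the multiplicity-adjusted list. If either failed, the point would need to be reopened. Nothing visible suggests that either does.
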